### **BNA Analysis**

All BNA recordings will be transmitted to EIMindA for analysis.

We will use a receiver operating characteristic (ROC) curve to assess the ability of each EEG BNA group pattern to discriminate MDD cases from controls using individual BNA similarity indices. The ROC analysis uses each value across the entire range of the EEG BNA pattern as the cut-off for defining a case and compares this classification to the “true” diagnosis, as defined by the structured diagnostic interview. The ROC curve plots the sensitivity versus the false positive rate (1-specificity) across the entire range of cut-offs. This analysis generates a statistic called the area under the curve (AUC), which is proportional to the overall ability of the scale across its range of cut-offs to correctly identify both cases and non-cases.

Secondly, we will analyze the results of EEG measurement during the test within patients to identify possible predictors of treatment response. Those analyses are exploratory in nature, and they could potentially lead to develop an EEG biomarker to predict antidepressant response.

In the first stage EEG signals are pre-processed using standard methods of blind source separation followed by band pass filtering into overlapping physiological frequency bands, epoched and averaged to result with ERPs. For each band, the data is reduced into a set of discrete points that denote local extrema, the latencies and (z-score normalized) amplitudes of which are inputted to the algorithm. These activity peaks naturally contain the major conventional ERP components, but all other associated and induced peaks as well, which fully represent the significant information in the measured data. For each experimental state (i.e. pre- and post-treatment, monotherapy vs. adjunctive therapy, healthy control vs. MDD), the algorithm then searches for peaks that have latencies synchronous across subjects. Next, peak-pair patterns are identified, whether within a single electrode or between any two, such that the inter-peak intervals were also synchronous across subjects. More complicated patterns of 3 or more peaks are sought in a similar manner, until a state-unique multi-sited spatio-temporal pattern or several distinct patterns emerge – the BNA group network.

In addition, BNA change analysis will be performed. Each subject participating in the drug treatment arm of the study is assigned similarity indices that quantify the degree to which his/her individual BNA repertoire match that of each group BNA. The score is computed twice for each subject – once for pre-treatment, and once for post-treatment, the difference between them being termed 'BNA change'.

## **Safety Analyses**

### **Adverse Events**

- Spontaneously reported AEs will be investigator-evaluated and documented throughout the study.
- The definition of treatment-emergent adverse events (TEAEs) will be provided in the statistical analysis plan (SAP).
- AEs that were reported more than once by a subject during the same period will be counted only once for that subject and period at the maximum severity.

### **Clinical Evaluations**

- Absolute values and changes from screening/Baseline in clinical safety laboratory tests, vital signs, ECG parameters, and weight will be summarized for each treatment group using descriptive techniques. Values outside normal ranges and potentially clinically significant values will be flagged and tabulated.
- Physical examination findings will also be summarized for each treatment group.

## **RISK/SAFETY INFORMATION**

EEG recording is a safe and non-invasive diagnostic procedure with no significant risk for the health of subjects. The EEG system complies with the standard electrical safety (EN 60601-1) and electromagnetic (EMC) compatibility and has received FDA clearance. Staff will be trained to minimize the discomfort associated with electrodes placement. Subjects will be able to communicate with staff throughout the procedure. The recording will be discontinued if the subject will indicate that she has become uncomfortable.

Memory and thinking tests can sometimes make subjects tired or uncomfortable. The study staff will try to make all subjects as comfortable as possible. Subjects will be informed that they do not have to answer any questions they choose not to answer.

**Antidepressant medication (vortioxetine)**

At the time of informed consent, the subject will be instructed about the risks and benefits of the vortioxetine that will be used throughout the study.

The potential risks of the medication will be based upon the FDA-approved package insert labeling for vortioxetine and will include, but not limited to, spontaneous reported adverse events and potential serious adverse events. Source documents will contain documentation that the subject was informed of risks of treatment and that there was adequate time to read and discuss this information with the clinician during the informed consent process.

The FDA-approved package insert for vortioxetine recommends a starting dose of 10 mg/day, increased to 20 mg/day as tolerated. The maximum dose is 20 mg/day, and the minimum dose is 5 mg/day if a higher dose is not tolerated. This allows for individualized “flexible” dosing for efficacy and tolerability.

In order to standardize this flexible dosing, all subjects will be started at 10 mg/day following visit 2 (baseline). The dose will be increased to a maximum of 20 mg/day after visit 4 (2 weeks of treatment) if tolerated by the subject. Dose decreases may occur at any time until Visit 8 for tolerability issues, to a minimum dose of 5 mg/day, and the dose may be re-increased if the tolerability issue resolves.

No dose adjustments may take place after visit 8 through the end of treatment (Visit 10).

Safety, tolerability, and depressive symptoms/function assessments will occur at baseline and each subsequent visit through the end of the study. While this is an exploratory analysis, the impact of treatment at various points in the study will be analyzed. Baseline assessments will occur prior to the subject receiving medication.

Drug accountability will be recorded at all visits. Subjects failing to meet at least 80% adherence to study medication between study visits will be discontinued from the study.

**Other Risks**

Whenever a subject is determined to be at risk for suicide during a clinical visit by the examining clinician, she or he will be escorted to the nearest emergency room.

We will not share information about subjects' participation in this study with others to minimize risks relative to subjects' privacy. Every effort will be made to keep participation confidential. These issues will be clearly stated in consent forms and discussed with participants during the informed consent procedure.

Consistent with good clinical practice, safety will be monitored by each subject's assigned clinician at each study visit. This clinician will be available 24 hours a day by page. The PI will supervise all study activities including ratings, reported adverse events, laboratory tests, and vital signs. Subjects will be monitored for adverse events at each visit and during phone communications with the clinician. All adverse events will be recorded.

All procedures will aim to minimize subject discomfort, and no subject will be asked to engage in research procedures not outlined in the consent form. All adverse events will be reported to the PHRC according to PHRC guidelines.

Subjects who are judged to experience a worsening of depressive symptoms as manifested by a CGI-Improvement rating of 6 or more (1=Very much improved, 2=Much improved, 3=Minimally improved, 4=No change, 5=Minimally worse, 6=Much worse, 7=Very much worse) or per the investigator's opinion for 2 consecutive visits the subject may be removed from the study and provided referrals as appropriate.

Subjects with MDD will be offered three months of follow-up care at the completion of the study (or if they are required to discontinue for any reason) in which they will be seen by study staff for routine outpatient management of their MDD. Subjects will receive referrals to clinicians in their communities, either at the end of the 3 month period, or sooner upon their request or circumstances require such a referral as determined by the investigator.

If a subject becomes pregnant or is found to be abusing substances during the study, he or she will be discontinued from the study and given referrals.

If a subject would like to have their clinical history forwarded to his/her primary care physician, or a new clinician, we will forward any pertinent information upon completing release forms in compliance with Good Clinical Practice Guidelines. If a subject was referred from a health care provider that is appropriate for follow-up care, the investigator may offer this among other possible referrals after the last study visit.

#### **EXPECTED BENEFITS**

Potential benefits to the participants include a thorough assessment by an expert clinician, education about the disorder, a treatment for MDD that could be continued after the study, and the opportunity to contribute to medical science and thus help others with the disorder.

#### **MONITORING/REPORTING OF AE/SAE COLLECTION AND RECORDING:**

*Adverse event* means any untoward medical occurrence associated with the use of a drug in humans, whether or not considered drug related.

*Life-threatening adverse event or life-threatening suspected adverse reaction.* An adverse event or suspected adverse reaction is considered "life-threatening" if, in the view of either the investigator or sponsor, its occurrence places the patient or subject at immediate risk of death. It does not include an adverse event or suspected adverse reaction that, had it occurred in a more severe form, might have caused death.

*Serious adverse event or serious suspected adverse reaction.* An adverse event or suspected adverse reaction is considered "serious" if, in the view of either the investigator or sponsor, it results in any of the following outcomes: Death, a life-threatening adverse event, inpatient hospitalization or prolongation of existing hospitalization, a persistent or significant incapacity or substantial disruption of the ability to conduct normal life functions, or a congenital anomaly/birth defect. Important medical events that may not result in death, be life-threatening, or require hospitalization may be considered

serious when, based upon appropriate medical judgment, they may jeopardize the patient or subject and may require medical or surgical intervention to prevent one of the outcomes listed in this definition. *Suspected adverse reaction* means any adverse event for which there is a reasonable possibility that the drug caused the adverse event. For the purposes of IND safety reporting, “reasonable possibility” means there is evidence to suggest a causal relationship between the drug and the adverse event. Suspected adverse reaction implies a lesser degree of certainty about causality than adverse reaction, which means any adverse event caused by a drug.

*Unexpected adverse event or unexpected suspected adverse reaction.* An adverse event or suspected adverse reaction is considered “unexpected” if it is not listed in the investigator brochure or is not listed at the specificity or severity that has been observed; or, if an investigator brochure is not required or available, is not consistent with the risk information described in the general investigational plan or elsewhere in the current application, as amended. “Unexpected,” as used in this definition, also refers to adverse events or suspected adverse reactions that are mentioned in the investigator brochure as occurring with a class of drugs or as anticipated from the pharmacological properties of the drug, but are not specifically mentioned as occurring with the particular drug under investigation.

While reports of pregnancy and overdose are not adverse experiences as defined above, notifications of these events will be made per procedure defined by IRB requirements and in accordance with further practice as designated by the PI.

Any adverse event that is ongoing when a subject completes his/her participation in the study must be followed until any of the following occurs:

- a. The event resolves or stabilizes;
- b. The event returns to baseline condition or value (if a baseline value is available); or
- c. The event can be attributed to agent(s) other than the study product, or to factors unrelated to study conduct.

#### **REPORTING TO IRBs AND REGULATORY AUTHORITIES:**

The sponsor must notify FDA in an IND safety report of potential serious risks, from clinical trials or any other source, as soon as possible, but in no case later than 15 calendar days after the sponsor determines that the information qualifies for reporting under paragraph (c)(1)(i), (c)(1)(ii), (c)(1)(iii), or (c)(1)(iv). The sponsor must submit each IND safety report in a narrative format or on FDA Form 3500A or in an electronic format that FDA can process, review, and archive. See §312.32 of the CFR for guidance.

#### **STUDY OVERSIGHT**

The Principal Investigator will be responsible for monitoring and assuring the validity and integrity of all data and adherence to the IRB-approved protocol. The study staff will monitor source data and case report forms by routine internal monitoring. BNA data will be monitored and interpreted by EIMindA in collaboration with the principal investigator, sub-investigator and study staff to assure BNA data is accurately collected.

The principal investigator and sub-investigators are responsible for monitoring the safety of the subjects who have entered this study and for alerting the IRB of any event that meets IRB reporting criteria. The investigator is also responsible to follow, through an appropriate health care option, adverse events that are serious or that caused the subject to discontinue before completing the study. The subject should

be followed until the event resolves or is explained. Frequency of follow-up is left to the discretion of the investigator.

### **Data and Safety Monitoring**

The principal investigator will be responsible for monitoring the safety of all subjects. In the event the principal investigator is unavailable, a sub-investigator will be available to monitor the safety of all subjects. Subjects will be evaluated throughout the study to assess comfort and safety. The principal investigator will be responsible for determining if a subject should be removed from the study. Subjects will be removed from the study if they decide to withdraw consent or are unable to tolerate the procedures due to anxiety and discomfort or if they develop a medical condition incompatible with their participation. The principal investigator will also terminate a subject's participation if they will determine that it is not in the subject's best interest.

### **IRB REVIEW/ETHICS/INFORMED CONSENT**

#### **IRB Review**

Prior to enrolling any subjects, documentation will be obtained that the study protocol and informed consent form have been approved by the Schulman Associates Institutional Review Board. Any change in the protocol or informed consent form will require prior written approval except to prevent injury or risk to a subject.

#### **Regulatory Considerations**

This study will be conducted in accordance with the ethical principles stated in the most recent version of the Declaration of Helsinki or the applicable guidelines on good clinical practice, whichever represents the greater protection of the individual.

#### **Recruitment**

The study population will be recruited from the greater Chicago metropolitan area. Subjects will be recruited from several sources, including referrals, responders to our general depression recruitment (advertisements on craigslist, newspapers, radio, the PMA website, private practice settings and community health centers). Subjects will also be recruited from ongoing clinical trials at Psychiatric Medicine Associates, LLC (PMA). Subjects may also be recruited from other trials only if considered appropriate for an open label treatment study with vortioxetine and do not meet other exclusion criteria. This is a study of depression in adults and therefore children will be excluded.

Subjects will be reimbursed for appropriate travel expenses during participation in the study.

### **GENERAL STUDY PROCEDURES**

All study personnel will have completed training for Good Clinical Practice guidelines prior to study initiation. There will be a start-up meeting on site for all study personnel prior to initiating the trial, including protocol review, study procedures, delegation of responsibility, recruitment, inter-rater reliability (for those who are involved in clinical ratings), and to review general study issues. Updates of the study will occur at weekly staff meetings, including internal monitoring of study-related documentation, enrollment updates, and to review amendments and/or serious adverse events.

All subject source documents and case report forms will be in written form and contained in a subject binder. Data for clinical patient/clinician assessments/outcomes will be entered into an electronic

database after review by the investigator/subinvestigator and internal monitor. Subjects will be assessed at each visit by investigator/subinvestigator to assure criteria are met to remain in the study. All study documents will be kept in a secure location and in compliance with GCP guidelines. Medication dispensing and recording of accountability will be done only by personnel who have authority (e.g., MD, PA). All medication will be kept in a double-locked, secure location in accordance with GCP guidelines and DEA requirements (for the investigational product). Temperature logs will be maintained daily and kept at a temperature recommended for the investigational drug.

#### **CONFIDENTIALITY**

All information collected about subjects for the purposes of this study will be treated as confidential to the extent allowed by law. The information obtained while subjects are enrolled in this study, including all study-related hospital and office records, will be made available to the study doctor, the study sponsor (Takeda), the Institutional Review Board and other regulatory agencies, including the United States Food and Drug Administration (U.S. FDA).

#### **Sending Specimens/Data to Research Collaborators Outside of PMA:**

EEG recordings, neurocognitive tests, depression outcomes and demographic data will also be sent to EIMindA Ltd headquarters in [name] for analysis. Any personal information and/or identifier will be removed to protect participants' identity and privacy.

EIMindA Ltd will have access to EEG data, study-related case report forms and questionnaires, and neurocognitive test results to perform BNA analysis (including electronic database information). Study documents and data will also be accessible by the study sponsor, Takeda.

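### The BNA vendor is given the clinical outcomes for its analysis, and nothing requires the BNA scores to be fixed before those outcomes are seen

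*Combined protocol and SAP*

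**What the plan says.** Under Sending Specimens/Data to Research Collaborators Outside of PMA, the protocol lists what leaves the site: "EEG recordings, neurocognitive tests, depression outcomes and demographic data will also be sent to EIMindA Ltd headquarters". It then gives the vendor's access and the purpose of that access: "EIMindA Ltd will have access to EEG data, study-related case report forms and questionnaires, and neurocognitive test results to perform BNA analysis". The electronic database is included. Personal identifiers are removed.

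Under BNA Analysis, the same vendor does the derivation: "All BNA recordings will be transmitted to EIMindA for analysis". The algorithm looks for peaks, then peak pairs, then larger patterns that are synchronous across subjects within an experimental state, "until a state-unique multi-sited spatio-temporal pattern or several distinct patterns emerge". The states named are "pre- and post-treatment, monotherapy vs. adjunctive therapy, healthy control vs. MDD". Each subject then receives "similarity indices that quantify the degree to which his/her individual BNA repertoire match that of each group BNA", before and after treatment, and the difference is the BNA change.

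Under Outcomes, the primary outcome relates BNA change to MADRS response status and to change in DSST. The Primary Efficacy Analysis section compares BNA change between groups defined by endpoint status, such as response, remission and DSST change.

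**The concern.** One party builds the score and, for the same work, holds the variables that the score will be compared with. The score is not a single predefined quantity: patterns come from the study's own data, more than one may emerge, and no index is designated as primary. Choices about preprocessing, which pattern to carry forward and which score component to report could therefore be made, even without intent, by someone who can see who responded.

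The stake is the primary BNA-outcome association. The pilot is meant to judge whether BNA gives clinically useful information and to help design a confirmatory study. An association that owes something to outcome-informed choices would look stronger than it is. A reader of the results could not separate scores fixed in advance from scores settled afterwards.

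**Working it through.** The plan gives no figure on this point: no sample-size calculation, no expected correlation and no number of BNA indices. The check is therefore mainly one of reading, followed by one illustration.

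**Reading the sections together**

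1. *Who derives the scores?* The vendor (BNA Analysis).
2. *Does that party receive the outcomes?* Yes. Depression outcomes and neurocognitive results are sent, and CRFs and questionnaires are accessible (Sending Specimens/Data).
3. *For what purpose?* The BNA analysis itself, not only a later correlation step.
4. *When?* Not stated. The documents do not say whether outcomes arrive before or after the scores are final.
5. *Are outcomes inputs to the pattern search?* Not according to the listed states, which do not include MADRS response or DSST status.
6. *Is there a safeguard?* No section provides vendor blinding, a firewall, a score lock, a prespecified index or a validation sample. Removing identifiers protects privacy and does not mask outcomes. Blind source separation is a signal-processing method.
7. *Does the derivation as described need outcomes?* No. The before/after state follows from the visit label, and every analysed subject has MDD by the entry criteria.

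**How many indices are available?** The Brain Network Activation part of the introduction lists score components for time (relative and absolute), amplitude and overall pattern, which can be read as four. The core battery has three event-related tasks, one of which may be dropped. That allows 4 × 3 = 12 combinations, or 4 × 2 = 8 with one task dropped, before counting stimulus types, frequency bands or multiple patterns. This shows that more than one index exists. It does not say how many would be examined.

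**Illustration**

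Assumptions: n = 40 (Number of Subjects) with no dropout; two-sided 5% Pearson test (Secondary Efficacy Analyses gives the level); no true association; the best of K indices reported; K assumed.

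- Critical correlation: t(0.975, 38) = 2.024, so |r| = 2.024 / √(38 + 2.024²) = 0.312.
- Independent indices: P(at least one p<0.05) = 1 − 0.95^K. For K=3 this is 1 − 0.857 = 0.143, for K=5 it is 1 − 0.774 = 0.226, and for K=10 it is 1 − 0.599 = 0.401.
- Indices correlated at 0.5: by simulation.

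| K | P(p<0.05), independent | P(p<0.05), correlation 0.5 | Mean best absolute r, independent | Mean best absolute r, correlation 0.5 |
|---|---|---|---|---|
| 1 | 5% | 5% | 0.13 | 0.13 |
| 3 | 14% | 13% | 0.21 | 0.20 |
| 5 | 23% | 18% | 0.25 | 0.23 |
| 10 | 40% | 29% | 0.30 | 0.27 |

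These are ordinary multiplicity figures. They show what selecting among indices can do. They do not measure what vendor access to outcomes will do. A fully blinded vendor who returned K locked scores, each tested at 5%, would give the same chance of at least one nominally significant result.

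**The case against.** The strongest reply has four parts.

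*The text gives access, not sequence.* BNA analysis may include the later correlation and prediction work, which needs outcomes. This stands. A reader might infer that the vendor holds the outcomes while it builds the patterns and that the scores are therefore contaminated. The documents do not support that. They leave the order open.

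*The search is algorithmic.* Its criterion is synchrony across subjects within a state, preprocessing is described as standard, and responder status is not a listed state. The introduction also describes a reference network model with named score components. This stands against any claim that outcomes enter the score. It does not close the gap, because the group networks come from this study's recordings, several patterns may emerge, and the choice of which pattern, task and component to report is not fixed.

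*The study is an exploratory, open-label pilot, and BNA change is also to be analysed independently of symptoms.* True, and this lowers the consequence. Exploration permits many analyses, but the reader still needs to know which scores were fixed before outcomes were seen. The primary outcome remains the link with MADRS response and DSST change.

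*The illustration is generic.* This stands in full. K is assumed, independence is unlikely for variants of one EEG, and a Pearson test suits DSST change better than binary MADRS response.

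A reader might also take Study Oversight, which has the vendor interpret BNA data together with the site team, as evidence of outcome-informed scoring. The stated aim of that sentence is accurate data collection, so it is not relied on here.

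**Conclusion.** The point holds as an unprotected risk. The vendor that derives and scores the BNA patterns is given the clinical and neurocognitive outcomes for that work, and no rule fixes the scores first. Outcome-informed choice is neither stated nor shown. It would be possible and would leave no trace, and if it occurred it would bias the primary association upward.

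The size is not determinable from the documents. The range of 14% to 40% for 3 to 10 independent indices (13% to 29% at a correlation of 0.5), against 5% for a single index fixed in advance, rests on an assumed K, n=40 with complete data and no true effect. It illustrates selection in general. A score lock without a named primary index would leave that multiplicity in place. The change should be made before any outcome data are transferred, because blinding cannot be restored afterwards. Confidence is moderate, since the vendor's own procedures are not in the documents.

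**What to change.** Amend Sending Specimens/Data to Research Collaborators Outside of PMA and BNA Analysis as follows:

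1. The vendor first receives only EEG files with subject code, visit label and technical recording data.
2. One primary BNA change index, defined by task and score component, is named in advance. All other indices are labelled exploratory.
3. Preprocessing, group networks and individual scores are locked, date-stamped and returned before clinical and neurocognitive outcomes, questionnaires and CRFs are released.
4. Any pattern or predictor derived after release is reported as post hoc.

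Items 1 and 3 deal with outcome-informed choice. Item 2 deals with multiplicity, which the lock does not touch.

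The cost is a transfer sequence, a lock step and a short delay. Predictor work that needs outcome labels comes second but is not lost. No extra subjects, visits or assessments are needed.
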